### **12.6.3 Efficacy data**

The efficacy data from Group 1, 6, 7 and 8 of the Continued Supply Expansion Phase will be summarised by dose, formulation (capsule or tablet) and schedule and is described below.

Summaries and waterfall plots of percentage change from baseline in sum of target lesions will be presented, and this data will also be analysed by analysis of covariance fitting baseline sum of target lesions as a continuous covariate and treatment group as a factor. Summary statistics will be presented for best overall response according to RECIST. PFS will be summarised using Kaplan-Meier estimates over time and will be displayed graphically.

Summaries of CA-125 response and the corresponding percentage change from baseline, will also be presented.

Summaries will be presented for the overall population and for the gBRCA ovarian cancer subgroup.

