**Table 4 Continued Supply Expansion Phase Secondary Objective**

Dependent Variables	Description
Steady State PK in Group 2	To generate PK data for both the capsule and the tablet formulation in the same patient to allow a direct comparison of the steady state pharmacokinetic parameters for capsule and tablet formulations.
Pharmacokinetics in Group 1, 3 4, 5, 5.1... 6, 7 and 8	To generate single dose (except Group 1) and steady state PK data for both the capsule and the tablet formulation in man. To obtain a preliminary assessment of the effect of food on the exposure to AZD2281 tablet Group 8 patients only).

**Table 4** Continued Supply Expansion Phase Secondary Objective

Dependent Variables	Description
Efficacy (Groups 1, 6, 7 and 8) Change from baseline in the sum of target lesions	Determined from radiological scans using RECIST criteria
Best overall response	Best tumour response determined by RECIST (CR, PR, SD or PD)
Progression-Free Survival	Progression free survival is defined as the time from randomisation to the earlier date of objective assessment of progression (per RECIST criteria) or death (by any cause in the absence of progression)
CA-125 Response	CA-125 response determined by GCIG criteria

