#### **4.1.2.4 Randomised comparison between tablet and capsule**

Following the completion of the dose escalation tolerability assessment up to 400 mg bid AZD2281, approximately 45 patients will be randomised to Group 6 to assess the multiple dose safety profile of the Melt-extrusion (tablet) formulation in a comparative setting. The patients will be randomised on a 1:1:1 ratio to the following active treatment arms:

- Treatment A: A tablet dose between 250mg and the higher tablet dose taken into the expansion that has been shown to be safe and tolerable
- Treatment B: 400 mg bid dosing with AZD2281 Gelucire® 44/14 (capsule) formulation
- Treatment C: 400 mg bid AZD2281 tablet dose (or lower if 400 mg bid is not tolerated).

If dose escalation continues beyond 400 mg bid, following the completion of the dose escalation tolerability assessment up to a dose defined by the SRC, approximately 30 patients may be randomised to Group 7 to assess the multiple dose safety profile of the Melt-extrusion (tablet) formulation in a comparative setting. The patients will be randomised on a 1:1 ratio to the following active treatment arms:

- 
- Treatment A: The highest bid tablet dose deemed tolerable by the SRC following the dose escalation phase
  - Treatment B: 400 mg bid capsule

Randomisation will be stratified based on primary tumour type (breast cancer or ovarian cancer). There must be at least 10 gBRCA ovarian patients in each arm.

Regardless of the formulation the patient is treated with or the treatment group assigned to, all patients may receive continuous treatment with the assigned formulation for as long as they remain free from intolerable toxicity and, in the Investigator's opinion, are receiving some clinical benefit from AZD2281 and do not meet any other discontinuation criteria.

Patients who experience NCI-CTCAE of grade 3 or 4 toxicity and meet the criteria outlined in Section 5.5.1 for AZD2281 will have their study medication stopped. The safety follow-up should be continued as outlined in the study schedule.

Once patients receiving AZD2281 have been discontinued from study medication, other treatment options will be at the discretion of the Investigator.

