## **12.3 Calculation or derivation of efficacy variable(s)**

A secondary objective of the Continued Supply Expansion Phase is to summarise the efficacy of AZD2281 on patients who receive tablet compared to patients who receive capsules. This will be achieved by measuring the % change in tumour burden compared with baseline, Best Objective Response, PFS and CA-125 response. Analyses will be performed in the overall population and in the gBRCA ovarian cancer subgroup.

The RECIST criteria will be used to programmatically determine % change in tumour burden compared with baseline, Best Objective Response and PFS.

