### **Dose escalation phase within the continued supply expansion**

The number of patients taking part in this part of the study will be approximately 185.

The primary objective of the dose escalation phase of the continued supply expansion is to determine the safety and tolerability profile of higher doses than 200 mg bid, of the melt-extrusion (tablet) formulation in groups of a minimum of 6 patients – (Groups 3 onwards) and to compare the safety and tolerability profile of higher doses than 200 mg bid, of the melt-extrusion (tablet) formulation with 400 mg bid Gelucire® 44/14 (capsule) formulation of AZD2281 in approximately 45 gBRCA ovarian and breast cancer patients (Group 6) and in 30 gBRCA ovarian and breast cancer patients (Group 7). The primary objective in the randomised tablet formulation continued supply expansion phase (Group 8) is to determine the safety and tolerability profile of selected tablet dose schedules of the melt-extrusion (tablet) formulation. No formal statistical comparisons of safety data will be performed. Instead, data will be listed and summarised descriptively by dose.

The secondary objectives of the dose escalation within the continued supply expansion will involve:

- All patients from Groups 3 onwards contributing to an assessment of the single dose and steady state exposures achieved with higher doses than 200 mg bid of AZD2281 melt-extrusion (tablet) formulation and all patients from Group 6 and 7 contributing to a comparison between patients of single dose and steady state exposures of AZD2281 achieved with selected tablet doses and the 400 mg bid capsule dose. Plasma concentration data and PK parameters will be listed and summarised descriptively using the appropriate standard summary statistics.
- A preliminary assessment of the effect of food by comparison of the Day 8 and Day 1 Cmax and AUC0-24 data from patients in the 400 mg od cohort of Group 8.
- To describe the efficacy data observed in patients treated with the Gelucire® 44/14 (capsule) and the Melt-extrusion (tablet) formulations. Summaries and waterfall plots of percentage change from baseline in sum of target lesions will be presented, and this data will also be analysed by analysis of covariance fitting baseline sum of target lesions as a continuous covariate and treatment group as a factor. Summary

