#### **12.4.5 Determination of sample size**

This study is an investigation of the comparative bioavailability of a new Melt-Extrusion (tablet) formulation of AZD2281 compared to the current Gelucire® 44/14 (capsule) formulation. There are no formal statistical analyses of the data planned and no formal sample size calculations have therefore been performed. The size of this study is based upon the desire to gain adequate PK information on the Melt-Extrusion (tablet) formulation whilst exposing as few patients as possible to study procedures.

Within the continued supply expansion phase, tablet doses (commencing at 250 mg bid) with potentially higher average exposure values than the 400 mg capsule dose will be explored and thus, in group 6 and 7 of the continued supply expansion, approximately 15 patients per arm (including at least 10 gBRCA ovarian cancer patients) are required to assess the safety and tolerability of these doses. In addition, as an exploratory measure of clinical activity, to rule out a significant difference between the melt-extrusion (tablet) formulation and the Gelucire® 44/14 (capsule) formulation, change in tumour size at eight weeks will be compared between the tablet dose arm(s) and the 400 mg bid capsule dose arm.

In Group 8, approximately 15 patients per treatment arm will be randomised. In a similar way as per the earlier expansion groups, change in tumour size will be evaluated.

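### Section 12.6.3 groups efficacy by dose, formulation and schedule with no term for randomised Group, so it permits a tablet–capsule contrast against capsule patients from other randomisations

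*Protocol*

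**What the plan says.** Randomisation is done separately within each Group. Group 1 (about 20 patients) is 1:1, 200 mg bid tablet against 400 mg bid capsule (Section 4.1.2.2). For Group 6 (about 45), Section 4.1.2.4 says "The patients will be randomised on a 1:1:1 ratio to the following active treatment arms": two tablet doses and 400 mg bid capsule. Group 7 (about 30, optional) is 1:1, a higher tablet dose against 400 mg bid capsule. Group 8 (about 60) is 1:1:1:1 among four tablet schedules, with no capsule arm.

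Table 4 limits efficacy to these four Groups. Section 12.6.3 says: "The efficacy data from Group 1, 6, 7 and 8 of the Continued Supply Expansion Phase will be summarised by dose, formulation" and schedule. The tumour-size model is an "analysis of covariance fitting baseline sum of target lesions as a continuous covariate and treatment group as a factor". Group is neither a summary level nor a model term.

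The synopsis gives the same model under three headings: Groups 1 and 2, Groups 3-7, and Group 8. Section 12.4.5, on Groups 6 and 7, says that "change in tumour size at eight weeks will be compared between the tablet dose arm(s) and the 400 mg bid capsule dose arm".

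For safety, the synopsis (Groups 3-7) and Section 12.4.2.7 say: "No formal statistical comparisons of safety data will be performed. Instead, data will be listed and summarised descriptively by dose". Section 12.6.2 summarises adverse events by treatment and laboratory, pulse and blood pressure data by dose and formulation, with the summaries to be built to suit the cohorts.

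**The concern.** Randomisation protects a comparison only among patients who could have been allocated to either arm. A capsule patient in Group 1 could never have received a Group 6 tablet dose.

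The protocol itself shows that the Groups may differ. They are recruited in sequence. Centres grow from a few in the UK to 6-8 in the UK plus 4-6 in Europe and Australia. Groups 6 and 7 require at least 10 ovarian patients per arm and may close to breast cancer patients early (Section 6.1.1), whereas no such minimum is stated for Group 1. If the capsule arms are merged, differences in calendar time, centre and tumour mix are counted as formulation or dose effects.

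The contrast is used for more than description. Section 12.4.5 compares tumour size at eight weeks to exclude a significant difference between formulations. Section 6.2.3.2 lets patients on a less effective arm move to a more effective one when the data show a significant difference.

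For safety, dose alone does not distinguish Group 6 capsule from Group 6 tablet when both are 400 mg bid. Nor does it distinguish randomised patients from non-randomised escalation patients on the same tablet dose.

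**Working it through.** **The plan's own figures.** The synopsis gives up to about 135 patients in Groups 6, 7 and 8: 45 + 30 + 60 = 135. Per arm: 45/3 = 30/2 = 60/4 = 15. These reproduce. The protocol gives no power calculation, alpha or SD for the tumour-size comparison.

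**Which arms share a cell.** The 400 mg bid capsule arms hold 10 patients (20/2, Group 1), 15 (Group 6) and 15 (Group 7, if run). Sorted by dose, formulation and schedule they fall in one cell: 10 + 15 = 25 without Group 7, or 10 + 15 + 15 = 40 with it. Under the synopsis heading for Groups 3-7 the cell would be 15 + 15 = 30.

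**Share not randomised against a Group 6 tablet arm, and its effect.** Suppose the other Groups' mean differs from Group 6 by d, with no true formulation effect. The contrast is then biased by share × d. Precision, in units of the residual SD, is SE = √(1/15 + 1/m) for a comparator of m patients.

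| Capsule comparator | m | Share from other Groups | Bias if d = 10 percentage points | SE (SD units) |
|---|---|---|---|---|
| Group 6 only | 15 | 0 | 0 | √(1/15 + 1/15) = 0.365 |
| Groups 1 + 6 | 25 | 10/25 = 40% | 4.0 | √(1/15 + 1/25) = 0.327 |
| Groups 6 + 7 | 30 | 15/30 = 50% | 5.0 | √(1/15 + 1/30) = 0.316 |
| Groups 1 + 6 + 7 | 40 | 25/40 = 63% | 6.25 | √(1/15 + 1/40) = 0.303 |

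The Group 1 tablet arm fares worse in the pool of 40: 30/40 = 75% were not randomised against it.

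**Effect on a nominal test.** The 5% two-sided level is supplied here for illustration; the protocol sets none. With the pool of 40 and d = 0.5 SD, bias = 0.625 × 0.5 = 0.3125 SD and bias/SE = 0.3125/0.303 = 1.03. The chance of rejecting with no true effect is then P(Z > 1.96 − 1.03) + P(Z < −1.96 − 1.03), about 18%. Two simulations of 4,000 trials each gave about 17%. With Group as a factor, rejection stayed between about 4% and 5.4% across the shifts tried. With the pool of 25, bias = 0.4 × 0.5 = 0.20 SD, bias/SE = 0.20/0.327 = 0.61, and the figure is about 9%.

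**Safety wording.** By dose alone, a 400 mg bid row could hold Group 6 capsule (15), Group 6 tablet (15) and Group 5.1 escalation tablet patients (at least 6). Dose and formulation together, as in Section 12.6.2, separate capsule from tablet but do not by themselves separate the Group 6 tablet arm from Group 5.1. Only the cohort wording in that section would do so.

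**The case against.** The strongest reply is that pooling is never ordered. Treatment group is undefined and can mean the randomised arm. The synopsis sets out the model under separate headings, and the contrast in Section 12.4.5 reads naturally as one within a Group. Groups 1, 6 and 7 share the same gBRCA entry criteria, so they may differ little. Group 7 is optional. Section 12.4.1 leaves details of listings and summaries to the SAP. All of this is fair, and it is why the point is that the text permits pooling, not that pooling will occur. It does not remove the point: Section 12.6.3 itself fixes the summary level and the model terms, and the synopsis heading for Groups 3-7 still places two separately randomised Groups under one model.

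A reader might also infer three stronger things that the documents do not support:

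- That safety is modelled across Groups. It is descriptive only. Section 12.6.2 adds formulation and cohort wording, and the synopsis summarises Group 8 by dose schedule.
- That non-randomised patients enter the efficacy analysis. Table 4 reads "Efficacy (Groups 1, 6, 7 and 8) Change from baseline in the sum of target lesions", and all four Groups are randomised. Escalation patients contribute to safety and PK summaries only.
- That all tablet patients are to be contrasted with all capsule patients, Group 8 included. Section 12.3 says that an objective is to "summarise the efficacy of AZD2281 on patients who receive tablet compared to patients who receive capsules", but this paraphrases an objective in a section on deriving variables. Section 12.6.3 splits by dose and schedule as well, which is incompatible with one tablet pool. The special eligibility rules of Group 8 therefore do not bear on the capsule contrast.

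**Conclusion.** The point holds as a weakness in fixed wording. Section 12.6.3, and the synopsis for Groups 6 and 7, permit a comparator in which 40% to 63% of capsule patients were not randomised against a given Group 6 tablet arm. The share rests on the planned arm sizes and on whether Group 7 is run. The resulting bias is that share times the difference between Groups. The size of that difference is an assumption (10 percentage points or 0.5 SD above), and the protocol gives no figure for it; if the Groups do not differ, there is no bias.

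The weight is moderate. Efficacy is secondary and exploratory, but the comparison can bear on arm switching, and an analysis matching the randomisation is available without new data. The safety element is narrower: three descriptions of the same tables need reconciling.

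**What to change.** In Section 12.6.3, the synopsis text for Groups 3-7 and Section 12.4.2.7:

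- State that tablet–capsule efficacy contrasts are made between randomised arms within each Group or, if Groups are combined, with Group as a factor in the ANCOVA.
- State that Group 8 contributes no tablet–capsule contrast.
- Label any summary that pools the same dose and formulation across Groups as supportive and non-randomised.

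For the descriptive safety summaries, bring the by-dose wording in the synopsis (Groups 3-7) and Section 12.4.2.7 into line with the dose, formulation and cohort wording of Section 12.6.2. Group 6 capsule and tablet arms at 400 mg bid, and non-randomised escalation patients, should each have their own column.

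The cost is wording and table layout, with no new data. A within-Group contrast of 15 against 15 has a standard error of about 0.37 SD, against 0.30 SD for 15 against a pool of 40: about a fifth wider (0.365/0.303 = 1.21). The narrower figure belongs to a contrast that randomisation does not protect.

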#### **4.1.2.2 Continued Supply Expansion Phase**

Once the PK team at AstraZeneca have confirmed the exposure ratio between the Gelucire® 44/14 (capsule) and Melt-extrusion (tablet) formulations, approximately 26 additional patients will be recruited to the Continued Supply Expansion Phase:

- Approximately 20 gBRCA patients will be recruited to Group 1 to assess the multiple dose safety profile of the Melt-extrusion (tablet) formulation in a comparative setting. The patients will be randomised on a 1:1 ratio to the following active treatment arms:
  - Treatment A: 200 mg bid AZD2281 Melt-extrusion (tablet) formulation
  - Treatment B: 400 mg bid AZD2281 Gelucire® 44/14 (capsule) formulation
  - Randomisation will be stratified based on primary tumour type (breast cancer or ovarian cancer).
- 6 patients will be recruited to Group 2 which will directly compare the steady state PK of the capsule and the Melt-extrusion (tablet) formulation. The patients will be randomly assigned a treatment sequence as follows:
  - Treatment Sequence 1: 200 mg bid AZD2281 Melt-extrusion (tablet) formulation until Day 8 followed by 400 mg bid AZD2281 Gelucire® 44/14 (capsule) formulation until Day 15

- 
- Treatment Sequence 2: 400 mg bid AZD2281 Gelucire® 44/14 (capsule) formulation until Day 8 followed by 200 mg bid AZD2281 Melt-extrusion (tablet) formulation until Day 15
  - After Day 15, all 6 patients will receive 200 mg bid AZD2281 melt-extrusion (tablet) formulation until treatment discontinuation.

[figure not shown]

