#### **6.1.1 Procedures for randomisation**

Eligible patients will be randomised in a 1:1 ratio (Sequence 1: Sequence 2) for Cohorts 1, 2 and 3 and Group 2 of the Continued Supply Expansion Phase. The actual treatment sequence given to individual patients will be determined by separate randomisation schemes for each cohort.

Eligible patients will be randomised in a 1:1 ratio (Treatment A: Treatment B) for Group 1 of the Continued Supply Expansion Phase.

Eligible patients will be randomised in a 1:1 or 1:1:1 ratio (Treatment A: Treatment B: and Treatment C (if applicable)) for Group 6 of the Continued Supply Expansion Phase.

Eligible patients will be randomised in a 1:1:1:1 ratio (Schedule A: Schedule B: Schedule C: Schedule D) for Group 8, Randomised Tablet Formulation Continued Supply Expansion Phase.

A blocked randomisation will be generated and all centres will use the same list in order to minimise any imbalance in the number of patients assigned to each treatment group. The randomisation scheme will not be stratified for the randomisation of treatment sequences. However, the randomisation of treatment arms for Group 1, 6 and 7 patients in the Continued Supply Expansion Phase will be stratified according to primary tumour type (either breast cancer or ovarian cancer). For Group 6 and 7 both gBRCA breast and gBRCA ovarian patients will be randomised. However, there should be at least 10 gBRCA ovarian patients enrolled per treatment arm; therefore recruitment may be closed to non-ovarian cancer patients before ovarian cancer patients.

Patient eligibility will be established before treatment randomisation. Patients will be randomised strictly consecutively, as patients are eligible for randomisation. Once the eligibility of a patient has been confirmed, the Investigator (or nominated assistant) should contact the Centralised Randomisation Centre by telephone for allocation of randomised treatment sequence or treatment arm and randomisation number. Patients will be identified to the Centralised Randomisation Centre using patient initials, enrolment number and date of birth and which Group the patient is intended to be randomised in to. The Centralised Randomisation Centre will inform the Investigator of the treatment sequence or treatment arm to be allocated to the patient at the randomisation visit.

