statistics will be presented for best overall response according to RECIST. PFS will be summarised using Kaplan-Meier estimates over time and will be displayed graphically. Analyses will be performed in the overall population and in the gBRCA ovarian cancer subgroup.

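### The overall-population tumour-size ANCOVA for Groups 1, 6 and 7 leaves out primary tumour type, the factor by which these groups are randomised; if tumour type is prognostic, the intervals are modestly too wide

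*Protocol*

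**What the plan says.** The efficacy model is written out in full. Section 12.6.3 gives it as "analysis of covariance fitting baseline sum of target lesions as a continuous covariate and treatment group as a factor". Section 12.4.2.7 gives the same two-term model for Group 1 and for the dose escalation and expansion groups, and so do the synopsis paragraphs on Groups 1 and 2 and on Groups 3-7.

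The allocation is also described. For the treatment arms of Groups 1, 6 and 7, Section 6.1.1 says that randomisation "will be stratified according to primary tumour type (either breast cancer or ovarian cancer". Section 4.1.2.2 says the same for Group 1 ("Randomisation will be stratified based on primary tumour type (breast cancer or ovarian cancer"), and Section 4.1.2.4 for Groups 6 and 7. On the method, Section 6.1.1 says: "A blocked randomisation will be generated and all centres will use the same list". Block size is not stated.

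Section 12.4.5 plans, for Groups 6 and 7, "approximately 15 patients per arm (including at least 10 gBRCA ovarian cancer patients". Its exploratory measure of activity is that "change in tumour size at eight weeks will be compared between the tablet dose arm(s) and the 400 mg bid capsule dose arm". For the dose escalation and expansion groups, Section 12.4.2.7 adds: "Analyses will be performed in the overall population and in the gBRCA ovarian cancer subgroup". Section 12.6.3 likewise presents both populations. Group 8 enrols ovarian cancer only, so it has no tumour-type stratum.

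**The concern.** Stratified allocation balances tumour type across arms, so differences between breast and ovarian patients largely drop out of the treatment contrast. A model without tumour type does not credit this: any such difference stays in the residual variance and inflates the standard error. The estimate then varies less from trial to trial than its reported standard error implies.

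The protocol treats tumour type as important elsewhere. It stratifies on it, sets a minimum number of ovarian patients per arm in Groups 6 and 7, and repeats the analysis in ovarian patients. The two-term model is fixed explicitly and repeatedly, so this is a mismatch within the protocol and not a detail left to the SAP.

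At stake is the stated precision of the pooled tablet-versus-capsule comparison. Section 12.4.5 gives its aim as ruling out a significant difference between formulations. For that aim an inflated standard error is not automatically the safe direction, because a real difference becomes harder to detect.

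**Working it through.** The protocol gives no SD, effect, margin, power or interval level for this ANCOVA, so there is no figure of its own to reproduce beyond the arm sizes: 3 × 15 = 45 (Group 6), 2 × 15 = 30 (Group 7), 2 × 10 = 20 (Group 1, "Approximately 20 gBRCA patients will be recruited to Group 1"). These agree with the text.

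**Inputs from the protocol.** Two strata, breast and ovarian. In Groups 6 and 7, at least 10 of about 15 patients per arm are ovarian, so at most about 5/15 = 1/3 are breast. Group 1 has no such minimum.

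**Assumptions not in the protocol.** Breast share p = 1/3, with 20% as an alternative for Group 6; breast-ovarian difference d from 0 to 1.5 residual SD; baseline slope 0.4, with baseline independent of tumour type; blocks of 4 (two arms) or 6 (three arms); 95% intervals.

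**Approximation.** With balanced arms, omitting tumour type raises the residual variance from 1 to 1 + p(1−p)d², so the standard-error ratio is √(1 + p(1−p)d²).

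- p = 1/3, p(1−p) = 2/9: d = 0.5 gives √1.056 = 1.027; d = 1 gives √1.222 = 1.106; d = 1.5 gives √1.5 = 1.225.
- p = 0.2, p(1−p) = 0.16: d = 0.5 gives √1.04 = 1.020; d = 1 gives √1.16 = 1.077; d = 1.5 gives √1.36 = 1.166.

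The factor costs one residual degree of freedom: 41 to 40 in Group 6 (45 less intercept, two treatment terms and baseline), 27 to 26 in Group 7, 17 to 16 in Group 1.

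**Simulation.** Stratified permuted blocks, 3000 runs per setting, least squares with and without the tumour-type term. Mean interval width without the term divided by width with it:

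| Setting | d = 0 | 0.25 | 0.5 | 0.75 | 1 | 1.5 |
|---|---|---|---|---|---|---|
| Group 6, 1/3 breast | 0.998 | 1.006 | 1.027 | 1.062 | 1.109 | 1.229 |
| Group 6, 20% breast | 0.998 | 1.003 | 1.018 | 1.043 | 1.076 | 1.172 |
| Group 7, 1/3 breast | 0.996 | 1.004 | 1.025 | 1.061 | 1.105 | 1.226 |
| Group 1, 1/3 breast | 0.990 | 0.999 | 1.019 | 1.053 | 1.097 | 1.223 |

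Coverage of the nominal 95% interval without the term is 0.951-0.956 at d = 0.5, 0.963-0.971 at d = 1 and 0.974-0.979 at d = 1.5. With the term it is 0.947-0.956 at these values.

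**Imbalance and the estimate itself.** The mean absolute difference in breast share between two arms is 3-5 percentage points. At d = 1 and p = 1/3 the SD of the treatment estimate, without and with the term, is 0.379 and 0.376 (Group 6), 0.380 and 0.375 (Group 7), 0.466 and 0.458 (Group 1). The actual variability hardly changes; what changes is the reported standard error.

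**The case against.** The strongest reply is that nothing of consequence turns on this. The aim is to describe efficacy, the comparison is called exploratory, there is no formal sample-size calculation, and no decision rule is tied to this ANCOVA. The protocol gives no breast-ovarian difference in shrinkage, and both types are enrolled as one gBRCA population expected to benefit. The widening is about 3% or less up to d = 0.5, and a one-third breast share is close to the most that Groups 6 and 7 allow. Most patients in those groups are also analysed in the ovarian subgroup, where tumour type is constant. All of this stands and keeps the point minor. It does not correct the pooled model, which is still reported.

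Two stronger readings are tempting. A reader might infer that the pooled intervals are certainly too wide. The documents do not support that: it depends on an effect they do not quantify, and with no effect the two-term interval is 0-1% narrower. A reader might also infer that chance imbalance in tumour type is left uncorrected and biases the comparison. Blocking within strata already limits that imbalance. Early closure to non-ovarian patients (Section 6.1.1) applies to all arms and at most leaves an incomplete block; missing week-8 scans could add a little more.

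**Conclusion.** The point holds as a minor one about stated precision. The overall-population model for Groups 1, 6 and 7 omits the stratification factor, and nothing else in the protocol supplies it. The intervals are conservative only if tumour type predicts tumour-size change beyond baseline: about 2-3% too wide at a difference of 0.5 residual SD, 8-11% at 1.0 and 17-23% at 1.5. These sizes rest on the assumed difference, breast share, baseline slope and block sizes. The trade is uneven: the factor costs at most about 1% in width if tumour type is irrelevant, and brings coverage back to about 95% if it is prognostic.

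**What to change.** In Sections 12.4.2.7 and 12.6.3 and in the synopsis paragraphs on Groups 1 and 2 and on Groups 3-7, add primary tumour type (breast or ovarian, as randomised) as a factor in the overall-population ANCOVA for Groups 1, 6 and 7. Leave the Group 8 model and the ovarian subgroup analysis unchanged, since tumour type is constant there. The cost is one added model term and one residual degree of freedom. The variable is known at randomisation, so no new data are needed.
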